#### **5.10.4.3 12-item Neuropsychiatric Inventory (NPI-12)**

##### *5.10.4.3.1 Select domains of the 12-item Neuropsychiatric Inventory (NPI-12), including depression (dysphoria), apathy, hallucinations, and agitation/aggression.*

Each selected domain score will be analyzed similar to primary endpoint as described in Section [5.10.2.1](#). Change from baseline will be the dependent variable. Difference in the change from baseline to the end of double-blind treatment period (average of the week 12 and week 16 score) between the neflamapimod treatment group and placebo with corresponding SE and 2-sided 95% CI will be presented.

The domains include:

- Depression (dysphoria)
- Apathy
- Hallucination
- Agitation/aggression

In addition, NPI-12 total score, NPI-4 total score and NPI-10 total score will be analyzed similar to primary endpoint as described in Section [5.10.2.1](#). NPI-10 total score will also be analyzed for each subgroup of cholinesterase inhibitor therapy (Yes/No) separately, as described in Section [5.10.2.1](#) except cholinesterase inhibitor therapy covariate will be removed from the model.

##### *5.10.4.3.2 Change in hallucinations frequency x severity score within the NPI-12 in subjects who report hallucinations at baseline.*

Hallucination domain score in subjects who reported hallucination at baseline will be analyzed similar to primary endpoint as described in Section [5.10.2.1](#). Change from baseline will be the dependent variable. The average change from baseline to the end of the double-blind treatment period (average of the week 12 and week 16 score) between the neflamapimod treatment group and placebo with corresponding SE and 2-sided 95% CI will be presented.

QMD Ref: Worldwide-TMP-ST-054-1.0_Effective: 12Aug2022	Governing QMD: Worldwide-SOP-ST-026
Confidentiality Statement	
This document is the property of Worldwide Clinical Trials Inc. and may not be duplicated, copied, altered or removed from company without prior approval from Worldwide Quality Assurance or in compliance with Worldwide Standard Operating Procedures.	

Worldwide Clinical Trials Controlled Quality Management Document		
 WORLDWIDE CLINICAL TRIALS	Sponsor:	EIP Pharma, Inc.
	Protocol Number:	EIP21-NFD-504
STATISTICAL ANALYSIS PLAN		

#### *5.10.4.3.3 Change in sleep and night-time behavior change within the NPI-12.*

Sleep and night-time behavior will be analyzed similar to primary endpoint as described in Section [5.10.2.1](#). Change from baseline will be the dependent variable. The average change from baseline to the end of the double-blind treatment period (average of week 12 and week 16) between the neflamapimod treatment group and placebo with corresponding SE and 2-sided 95% CI will be presented.

#### **5.10.4.4 Change in MDS-UPDRS3 motor examination (Part III) score**

MDS-UPDRS3 score will be analyzed similar to primary endpoint as described in Section [5.10.2.1](#). Change from baseline will be the dependent variable. The difference in the change from baseline during the double-blind treatment period between the neflamapimod treatment group and placebo with corresponding SE and 2-sided 95% CI will be presented.

#### *5.10.4.5 Change in beta functional connectivity and in alpha reactivity on quantitative EEG and Basal forebrain atrophy by structural MRI*

The EEG data will be analysed independently by CortiCare and the report will be provided to EIP. No analysis of EEG data will be included as part of this SAP. Similarly, MRI analysis will be defined separately, and it will not be a part of this SAP.

### **5.10.5 Multiplicity**

Secondary endpoints will be evaluated in a hierarchical manner. If the two-sided p-value for the comparison of neflamapimod and placebo for the primary endpoint (average change from baseline in CDR-SB during the double-blind treatment period) is  $\geq 0.05$ , the secondary endpoints will not be evaluated for statistical significance. If, on the other hand, the two-sided p-value for the primary endpoint is  $< 0.05$ , the difference between neflamapimod and placebo on the TUG will be evaluated utilizing a statistical threshold of  $p=0.05$  (i.e., neflamapimod will have demonstrated an effect on the TUG test if  $p<0.05$ ). If the two-sided p-value for the difference between neflamapimod and placebo in average change from baseline in the TUG test is  $< 0.05$ , then treatment effects on the NTB and the ADCS-CGIC will be independently evaluated using a local significance threshold of 0.025 (i.e. utilizing Bonferroni correction), such that neflamapimod will have demonstrated an effect for any of these two endpoints if the associated two-sided p-value is  $< 0.025$  for the comparison between neflamapimod and placebo for the respective endpoint.

### **5.11 Pharmacokinetic and Biomarker Analyses**

A listing of plasma trough concentrations will be presented for the PK Analysis Set. Plasma biomarker analysis will be defined separately and will not be part of this SAP.

QMD Ref: Worldwide-TMP-ST-054-1.0 Effective: 12Aug2022	Governing QMD: Worldwide-SOP-ST-026
Confidentiality Statement	
This document is the property of Worldwide Clinical Trials Inc. and may not be duplicated, copied, altered or removed from company without prior approval from Worldwide Quality Assurance or in compliance with Worldwide Standard Operating Procedures.	

Worldwide Clinical Trials Controlled Quality Management Document		
 WORLDWIDE CLINICAL TRIALS	Sponsor:	EIP Pharma, Inc.
	Protocol Number:	EIP21-NFD-504
STATISTICAL ANALYSIS PLAN		

Note: Glial Fibrillary Acidic Protein (GFAP) and Neurofilament light (NfL) levels will be measured in pre-treatment, week 12 and week 16 and the results analyzed for treatment effects concurrently with the primary efficacy analysis.

## 5.12 Safety Analyses

The safety analyses will be presented by the treatment received for the Safety Analysis Set for each treatment phase.

### 5.12.1 Adverse Events

The following tables will be presented for AEs. Incidence and/or number of events will be reported as appropriate:

- Overall summary of TEAEs
- TEAEs by system organ class and preferred term
- Treatment related TEAE by system organ class and preferred term
- Serious TEAE by system organ class and preferred term
- TEAE by system organ class, preferred term and maximum severity
- TEAE by system organ class, preferred term and closest relationship
- TEAEs leading to early withdrawal by system organ class and preferred term
- Listing of Serious TEAEs (presented in the Table section of the appendices).
- Listing of Deaths (presented in the Table section of the appendices).

AE incidence is counted only once per system organ class and once per preferred term. The number and percent of subjects experiencing events are reported. Outputs reported at maximum severity show the highest severity reported by a subject per system organ class and preferred term. MedDRA version 26.1 or higher will be used for coding purposes.

All AEs will be listed.

### 5.12.2 Laboratory Data

Descriptive statistics of the observed values and change from baseline (continuous data) will be presented by treatment group and visit for each hematology, chemistry, and coagulation parameter. Each measurement (continuous data) will be classed as below, within, or above normal range, based on ranges supplied by the laboratory used. Shift tables in relation to the normal range from baseline to each follow-up visit will be presented.

Further, number (%) of patients that meet the following cut-off points at baseline and each post-baseline visit will be presented:

- ALT >3 x ULN

QMD Ref: Worldwide-TMP-ST-054-1.0_Effective: 12Aug2022	Governing QMD: Worldwide-SOP-ST-026
Confidentiality Statement This document is the property of Worldwide Clinical Trials Inc. and may not be duplicated, copied, altered or removed from company without prior approval from Worldwide Quality Assurance or in compliance with Worldwide Standard Operating Procedures.	

Worldwide Clinical Trials Controlled Quality Management Document		
 WORLDWIDE CLINICAL TRIALS	Sponsor:	EIP Pharma, Inc.
	Protocol Number:	EIP21-NFD-504
STATISTICAL ANALYSIS PLAN		

- ALT >5 x ULN
- ALT >8 x ULN
- AST >3 x ULN
- AST >5 x ULN
- AST >8 x ULN
- ALT or AST >3 x ULN
- ALT or AST >5 x ULN
- ALT or AST >8 x ULN
- Total Bilirubin >1.5 x ULN
- Total Bilirubin >2 x ULN
- (ALT or AST >3 x ULN) and (Total Bilirubin > 2 x ULN or INR >1.5)\*

\*For multi-parameter categories, parameter values must be from the same sample (e.g., have same sample date).

All laboratory data will be listed.

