### 5.2.4 Early Withdrawal Assessments

For the analysis, assessments performed at early withdrawal visits will be mapped to the nearest missed visit, using midpoints between visits to window the early withdrawal. If the early withdrawal assessment is mapped to a visit where a scheduled assessment is already present, the scheduled assessment will take precedence, and the early withdrawal assessment will be disregarded (and listed only).

*Table 1: Early withdrawal mapping for scheduled visits of Double-Blind Treatment Phase*

Assessment(s)	Timing of Early Withdrawal Assessment	Mapped Visit
---------------	---------------------------------------	--------------

QMD Ref: Worldwide-TMP-ST-054-1.0_Effective: 12Aug2022	Governing QMD: Worldwide-SOP-ST-026	
Confidentiality Statement		

This document is the property of Worldwide Clinical Trials Inc. and may not be duplicated, copied, altered or removed from company without prior approval from Worldwide Quality Assurance or in compliance with Worldwide Standard Operating Procedures.

Worldwide Clinical Trials Controlled Quality Management Document		
 WORLDWIDE CLINICAL TRIALS	Sponsor:	EIP Pharma, Inc.
	Protocol Number:	EIP21-NFD-504
STATISTICAL ANALYSIS PLAN		

Physical Examination	Day 2 to Day 117	Week 16
	Day 118 to (Last dose+14 days)	Follow-Up
Vital Signs	Day 2 to Day 17	Week 2
	Day 18 to Day 33	Week 4
	Day 34 to Day 61	Week 8
	Day 62 to Day 89	Week 12
	Day 90 to Day 117	Week 16
	Day 118 to (Last dose+14 days)	Follow-Up
Hematology, Chemistry, C-SSRS, NTB, DCFS	Day 2 to Day 33	Week 4
	Day 34 to Day 61	Week 8
	Day 62 to Day 89	Week 12
	Day 90 to Day 117	Week 16
Coagulation, EEG	Day 2 to Day 117	Week 16
CDR-SB, TUG	Day 2 to Day 61	Week 8
	Day 62 to Day 89	Week 12
	Day 90 to Day 117	Week 16
NPI-12	Day 2 to Day 89	Week 12
	Day 90 to Day 117	Week 16
ADCS-CGIC	Day 2 to Day 117	Week 16
MDS-UPDRS	Day 2 to Day 61	Week 12
	Day 62 to Day 117	Week 16

Table 2: Early withdrawal mapping for scheduled visits of Open-Label Extension Phase

Assessment(s)	Timing of Early Withdrawal Assessment	Mapped Visit
Physical Examination	Day 2 to Day 229	Week 32
	Day 230 to (Last dose+14 days)	Follow-Up
Vital Signs	Day 2 to Day 33	Week 4
	Day 34 to Day 61	Week 8
	Day 62 to Day 117	Week 16
	Day 118 to Day 229	Week 32
	Day 230 to (Last dose+14 days)	Follow-Up
Hematology, Chemistry	Day 2 to Day 33	Week 4
	Day 34 to Day 61	Week 8
	Day 62 to Day 117	Week 16
	Day 118 to Day 229	Week 32
Coagulation	Day 2 to Day 229	Week 32

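### The liver cut-off table counts patients visit by visit only, so it cannot show how many ever crossed a threshold and can omit a peak at early withdrawal

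*SAP*

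**What the plan says.** SAP 5.12.2 lists single-parameter cut-offs for ALT, AST, ALT or AST, and total bilirubin, plus one combined category, ("ALT or AST >3 x ULN) and (Total Bilirubin > 2 x ULN or INR >1.5"). The counting rule is the "number (%) of patients that meet the following cut-off points at baseline and each post-baseline visit will be presented". A footnote to the combined category reads: "For multi-parameter categories, parameter values must be from the same sample (e.g., have same sample date". The results go in Tables 14.3.7.7a (double-blind) and 14.3.7.7b (open-label extension, OLE).

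Three other sections decide which samples reach which row:

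- 5.2.22 tabulates unscheduled post-baseline visits as well, each under its own 'Visit x.xx' label.
- 5.2.4 maps early-withdrawal assessments to a scheduled visit. If that visit already holds a scheduled assessment, the scheduled one is kept and the withdrawal one is only listed.
- Table 1 ("Early withdrawal mapping for scheduled visits of Double-Blind Treatment Phase") maps "Hematology, Chemistry, C-SSRS, NTB, DCFS" to Weeks 4, 8, 12 and 16, but "Coagulation, EEG" to Week 16 only. Table 2 maps "Hematology, Chemistry" to Weeks 4, 8, 16 and 32, but has a single coagulation line: "Coagulation Day 2 to Day 229 Week 32".

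**The concern.** A reader of a liver safety table first wants to know how many patients on each arm ever exceeded 3, 5 or 8 times the upper limit, and how many met the combined category. By-visit rows do not answer that. They cannot be added, because one patient may appear in several. The largest single row is only a lower limit, because different patients may appear in different rows.

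The SAP does count per patient elsewhere. Adverse events are counted once per preferred term and shown at maximum severity (5.12.1). Suicidal ideation and behaviour are defined as a positive answer at any time in the double-blind phase (5.2.21). The liver table has no equivalent.

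The withdrawal rule matters because a sample taken when a patient leaves the trial may hold that patient's highest value. That value can be missing from the table. For the combined category, the visit mapping can also place two results from one blood draw in different rows.

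**Working it through.** The SAP states no figure for this table, so there is none to reproduce. The inputs are the by-visit rule in 5.12.2, the mapping windows in Tables 1 and 2 of 5.2.4, and the day conventions in 5.2.5 and 5.2.6.

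**1. What by-visit rows say about incidence.** Let n_v be the number of patients over a cut-off in row v, N the arm size and M the number ever over it. The rows give only max(n_v) ≤ M ≤ min(N, Σ n_v). As an illustration, not an expected result, take 2 patients in each of the four scheduled chemistry rows with N = 80. Then M lies between 2 (2/80 = 2.5%) and 8 (8/80 = 10%). Each unscheduled row widens the range.

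**2. When a withdrawal sample drops out.** The first dose is Day 1, so an on-time Week w visit falls on Day 7w + 1. This is an assumption, because the protocol's visit windows are not shown.

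| Phase | On-time chemistry days | Mapping window ends |
|---|---|---|
| Double-blind | 29, 57, 85, 113 | 33, 61, 89, 117 |
| OLE | 29, 57, 113, 225 | 33, 61, 117, 229 |

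Each window ends 4 days after the on-time visit. A withdrawal sample in those 4 days maps to a visit already filled and is only listed. That is 4 × 4 = 16 of 116 possible days in the double-blind phase (13.8%) and 16 of 228 in the OLE (7.0%). The OLE count takes Table 2 days from the first open-label dose. A scheduled visit held early lengthens the gap. These are shares of calendar days, not probabilities.

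**3. Where same-date chemistry and coagulation go.**

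- Double-blind: the mapped visits agree only on Days 90-117. They differ on Days 2-89, which is 89 − 2 + 1 = 88 of 117 − 2 + 1 = 116 days (76%).
- OLE: they agree only on Days 118-229. They differ on Days 2-117, which is 116 of 229 − 2 + 1 = 228 days (51%).

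**4. A worked case.** A patient has on-time Week 8 chemistry on Day 57 and withdraws on Day 60, with chemistry and coagulation drawn together. The chemistry maps to Week 8, which is filled, so it is only listed. The coagulation maps to Week 16 and is kept. Suppose that on Day 60 ALT is above 3 x ULN and INR is above 1.5. The ALT value reaches no row. INR has no row of its own. The SAP does not say whether the pair counts in the combined category, or in which row, although both values share a sample date.

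**The case against.** The strongest case for the plan is that little is hidden. All laboratory values are listed (Listings 16.2.8.2 and 16.2.8.3), Table 14.3.4.1 reports abnormal values, and ALT, AST and bilirubin have cut-off rows of their own. The table shells are a separate document and are not shown, so a shell might already contain a cumulative row. The same-sample rule is deliberate, explicit and contradicted nowhere.

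Much of this stands. The gap is shown for the SAP text only, and the same-sample definition should stay. But a listing does not give a per-arm count, and the separate cut-off rows are themselves by visit.

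Two stronger readings are tempting. A reader might infer that the combined category fails at most visits because coagulation is mapped to only one of the four chemistry visits in each phase. The documents do not support that. INR is one side of an 'or', and if bilirubin is in the chemistry panel the category can be evaluated at all four visits. Where no INR was drawn, the rule discards nothing. A reader might also infer that an enzyme rise followed by a raised bilirubin or INR on a repeat sample is never counted. That is not so either: if ALT or AST is still above 3 x ULN on the repeat sample, the patient counts in that unscheduled row. Only pairs whose parts fall on different dates are left out, and that follows from the chosen definition.

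**Conclusion.** The point holds as a gap in safety reporting. On the SAP text, the liver table does not give the number of patients per arm who ever crossed a cut-off, and 5.2.4 can remove a value taken at withdrawal. For the combined category, the visit row for same-date withdrawal chemistry and coagulation is undefined on 88 of 116 double-blind days and 116 of 228 OLE days.

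This rests on three assumptions: the schedule read from Tables 1 and 2 matches the protocol, INR belongs to the coagulation panel, and the shells add no cumulative row. If bilirubin is in the chemistry panel, the mapping problem affects only the INR part. Without liver event rates, no number of missed patients can be given.

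**What to change.** In 5.12.2 and Tables 14.3.7.7a/b:

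- Add an any-post-baseline row per phase for every cut-off. Count each patient once over all scheduled, unscheduled and early-withdrawal samples, including withdrawal samples that 5.2.4 would only list.
- Evaluate the combined category by actual sample date before any visit mapping. Keep the same-sample definition, and state which visit row carries a withdrawal result.
- Optionally, list patients who met the ALT/AST part and the bilirubin or INR part on different dates. Set no fixed window, since the SAP gives no basis for one.

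The cost is a few descriptive rows from data already collected, with no effect on any test or on alpha. The existing addendum says the database is locked and the study unblinded, so the change belongs in a further addendum, as section 5 provides, with the rows marked as added after unblinding.

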### 5.12.3 Vital Signs

Descriptive statistics for observed values and changes from baseline in the following vital signs will be presented by treatment group and visit:

- Systolic blood pressure (mmHg)
- Diastolic blood pressure (mmHg)
- Pulse rate (bpm)
- Respiration rate (breath / min)
- Temperature (degrees Celsius)

### 5.12.4 Electrocardiogram Data

All ECG data collected at screening for variables listed below including details of any abnormalities, will be listed.

- Heart rate (bpm)
- PR interval (ms)
- RR interval (ms)
- QRS complex (ms)
- QT interval (ms)
- QTc interval (ms) [Fridericia's formula - QTcF]

QMD Ref: Worldwide-TMP-ST-054-1.0_Effective: 12Aug2022	Governing QMD: Worldwide-SOP-ST-026
Confidentiality Statement	

This document is the property of Worldwide Clinical Trials Inc. and may not be duplicated, copied, altered or removed from company without prior approval from Worldwide Quality Assurance or in compliance with Worldwide Standard Operating Procedures.

Worldwide Clinical Trials Controlled Quality Management Document		
 WORLDWIDE CLINICAL TRIALS	Sponsor:	EIP Pharma, Inc.
	Protocol Number:	EIP21-NFD-504
STATISTICAL ANALYSIS PLAN		

### 5.12.5 Physical Examination

The body systems within the physical examination data at the end of the study will be summarized by treatment (Normal; Abnormal NCS, Abnormal CS). A continuous summary of weight (kg) will be provided. Shift from baseline in body system results will also be tabulated.

All physical examination data will be listed.

### 5.12.6 Columbia-Suicide Severity Rating Scale

A shift summary of C-SSRS by treatment and visit will be provided. All C-SSRS data will be listed.

## 6 INTERIM ANALYSIS

No interim analysis is planned. The primary analyses will be performed after the blinded treatment phase of 16 weeks. Subjects may go on to a long term open-label extension and a final analysis will be performed with the additional long-term data.

## 7 DATA SAFETY MONITORING BOARD ANALYSIS

Data safety monitoring board (DSMB) analyses are described in the DSMB analysis plan.

## 8 CHANGES TO PLANNED PROTOCOL ANALYSIS

- A few changes made to the US protocol in v2.0 have not been made in Ex-US protocol v2.0. Hence there are few differences between the US and Ex-US protocols. In such cases, the SAP has followed details as in US protocol. E.g., Letter Fluency Test is not part of NTB as per US protocol v2.0.
- The exploratory objectives are reframed to provide more clarity on the objective of each endpoint being assessed as the statements in protocol only specified the scales of measurement and not the intent for assessing them.
- All endpoints are reframed to specify the analysis will be performed for the double-blind treatment period data.
- Primary objective wording has been changed from “to demonstrate the efficacy of neflamapimod, compared to placebo” to “to compare the efficacy of neflamapimod, with placebo”.
- Attention composite is added as exploratory endpoint instead of secondary endpoint.
- Exploratory endpoints for NPI-12 are reframed to specify average of Week 12 and Week 16 will be analyzed.
- The error in protocol regarding directionality of ADCS-CGIC score was corrected from “higher score indicates improvement” to “lower score indicates improvement”.

QMD Ref: Worldwide-TMP-ST-054-1.0_Effective: 12Aug2022	Governing QMD: Worldwide-SOP-ST-026
Confidentiality Statement  This document is the property of Worldwide Clinical Trials Inc. and may not be duplicated, copied, altered or removed from company without prior approval from Worldwide Quality Assurance or in compliance with Worldwide Standard Operating Procedures.	

Worldwide Clinical Trials Controlled Quality Management Document		
 WORLDWIDE CLINICAL TRIALS	Sponsor:	EIP Pharma, Inc.
	Protocol Number:	EIP21-NFD-504
STATISTICAL ANALYSIS PLAN		

- Efficacy analysis set was renamed as mITT Analysis Set.
- PK Analysis Set and completer analysis set was added.
- mITT Analysis Set, Safety Analysis Set were defined separately for double-blind treatment phase and open-label extension phase.

QMD Ref: Worldwide-TMP-ST-054-1.0 Effective: 12Aug2022	Governing QMD: Worldwide-SOP-ST-026
Confidentiality Statement This document is the property of Worldwide Clinical Trials Inc. and may not be duplicated, copied, altered or removed from company without prior approval from Worldwide Quality Assurance or in compliance with Worldwide Standard Operating Procedures.	

Worldwide Clinical Trials Controlled Quality Management Document		

## 10 LIST OF TABLES, FIGURES AND LISTINGS

The following table includes details of the tables, figures and listings to be included within each section of the eCTD. The eCTD section is shown in bold. The following validation methods may be used:

- Independent programming of numbers and manual review of format (IP)
- Independent programming by statistician of numbers and manual review of format (Stat IP)
- Manual review (MR)
- Code review (CR)

Table Number	Table Title	Validation Method	Shell Number (if repeat)	Topline
Items in bold are not table titles but references to the section headings within eCTD.				
14.1	Demographics Data			
14.1.1	Disposition			
14.1.1.1a	Subject Disposition – Double-Blind Treatment Phase - Screened Set	IP		Topline
14.1.1.1b	Subject Disposition – Open-Label Extension Phase - Full Analysis Set	IP		
14.1.1.2	Screen Failures - Screened Set	IP		
14.1.1.3	Inclusion / Exclusion Criteria Violation - Screened Set	IP		
14.1.1.4a	Recruitment by Site - Double-Blind Treatment Phase - Full Analysis Set	IP		
14.1.1.4b	Recruitment by Site - Open-Label Extension Phase - Full Analysis Set	IP	14.1.1.4a	
14.1.1.5	Visit Attendance - Full Analysis Set	IP		
14.1.1.6a	Protocol Deviations – Double-Blind Treatment Phase - Full Analysis Set	IP		
14.1.1.6b	Protocol Deviations – Open-Label Extension Phase - Full Analysis Set	IP	14.1.1.6a	
14.1.2	Demographics			
14.1.2.1	Demographics - Safety Analysis Set	IP		
14.1.2.2	Demographics - Full Analysis Set	IP	14.1.2.1	Topline
14.1.3	Baseline Characteristics			
14.1.3.1	Baseline Characteristics - Safety Analysis Set	IP		
14.1.3.2	Baseline Characteristics - Full Analysis Set	IP	14.1.3.1	Topline
14.1.3.3	Previous Medical History - Safety Analysis Set	IP		
14.1.3.4	Medical History Ongoing at Screening - Safety Analysis Set	IP	14.1.3.2	

QMD Ref: Worldwide-TMP-ST-054-1.0\_Effective: 12Aug2022

Governing QMD: Worldwide-SOP-ST-026

